3.2 Study Duration

Subjects will be assessed for up to 3 years post-treatment with ADVM-043. The duration of this long-term follow-up period is 2 years.

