6.9 Follow-up of Subjects Reporting an Adverse Event

SAEs related to ADVM-043 and AEs of interest should be followed until satisfactory resolution or until the Investigator deems the event to be stable.

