4.5 Treatment Allocation

Not Applicable.

5 Assessment Schedule

Subjects will be assessed for up to 3 years post-treatment with ADVM-043. The duration of this long-term follow-up period is 2 years.

Assessment ^a	Post-Treatment Assessment Timepoints			
	Screening ^b	Year 1	Year 2	Year 3 (EOS) ^c
ICF	X			
Inclusion/ Exclusion Criteria	X			
Review and record exposure to other investigational therapies	X	X	X	X
Record AEs of interest/related SAEs	X	X	X	X
Record conmeds ^d	X	X	X	X

Abbreviations: AE = adverse event; conmed = Concomitant medication; EOS = End-of-Study visit; ICF = Informed Consent Form; SAE = serious adverse event; [X] = optional.

^a Assessments may be conducted in the clinic or with a phone call by site personnel.

^b The Screening Assessment should be completed on the same day as the End-of-Study Visit in the prior ADVM-043 treatment study.

^c End-of-Study (EOS) Assessment is scheduled at 3 years post-treatment [REDACTED]; or within [REDACTED] after subject withdrawal.

^d Only concomitant medications for A1AT deficiency (i.e., augmentation therapy), known mutagenic medications / agents, and medications to treat AEs of interest and SAEs related to ADVM-043 should be recorded.

6 Interim Analysis

No interim analysis planned for this study.

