7.1 Primary Endpoint

1. *Type, frequency, severity, duration, and relationship to ADVM-043 of adverse events (AEs) of interest and serious adverse events (SAEs) related to ADVM-043.*

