8.1 Handling Missing/Incomplete Data

Missing data will not be imputed.

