10.6 Adverse Events Flags

An AE is any untoward medical occurrence in an enrolled subject, regardless of its causal relationship to the investigational medicinal product.

Only AEs of interest will be collected and reported in the current study. AEs of interest that are continuing from the previous study will be imported for long term follow-up.

AEs of interest include:

- new malignancy
- new incidence or exacerbation of a pre-existing neurologic disorder
- new incidence or exacerbation of a prior rheumatologic or other autoimmune disorder
- unexpected hospitalization

Study Period:

All AEs will be counted once under the below period in which the AE has started.

- Previous Study: Reported from AE (External).
- Screening – Year 1: If AE start date is after screening and on or before Year 1 visit date.
- Year 1 – Year 2: If AE start date is after Year 1 and on or before Year 2 visit date.
- Year 2 – Year 3 (EOS): If AE start date is after Year 2 and on or before Year 3 visit date.

Related Adverse Events:

- AE (External): includes Possibly, Probably and Definitely Related Adverse Events
- AE: includes Definitely and Likely Related Adverse Events.

Relationship to ADVM-043 will be flagged separately.

Severity:

Subjects with the same AE of interest and different severities will be flagged for the most intense severity. i.e., If the same event has been reported twice with severity 'Grade 1 – Mild' and 'Grade 3 – Severe' then the subject will be flagged as 'Grade 3 – Severe'. AEs that are missing severity will be presented in summary tables as 'Grade 3 – Severe'.

Duration of AEs:

Duration of Adverse events (days) will be calculated as follows: (AE End date – AE Start date) + 1.

For adverse events that are ongoing at end of study, date of end of study will be considered as AE End date.

11 Statistical Analyses

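### For adverse events still ongoing at end of study, SAP 10.6 reports a censored duration as a completed one, with no marker

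*SAP*

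**What the plan says.** SAP 7.1 defines the primary endpoint as "Type, frequency, severity, duration, and relationship to ADVM-043 of adverse events (AEs) of interest" together with related serious adverse events. No other endpoint is listed.

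SAP 10.6 is the only place where duration is derived: "Duration of Adverse events (days) will be calculated as follows: (AE End date – AE Start date) + 1". Its next sentence covers unresolved events: "For adverse events that are ongoing at end of study, date of end of study will be considered as AE End date". No censoring indicator accompanies the derived value. The same section imports AEs of interest that continue from the treatment study, so some start dates precede this study.

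Follow-up is limited: "Subjects will be assessed for up to 3 years post-treatment with ADVM-043" (SAP Section 5) and "The duration of this long-term follow-up period is 2 years" (Protocol 3.2). For completers, "End-of-Study (EOS) Assessment is scheduled at 3 years post-treatment". The same footnote gives a separate, partly redacted timing after withdrawal.

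Four other provisions bear on the rule:

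- Protocol 6.9 says that AEs of interest and related SAEs "should be followed until satisfactory resolution or until the Investigator deems the event to be stable".
- Protocol 4.3 asks sites for follow-up data on withdrawn subjects whose events are ongoing.
- Protocol 6.6 collects the resolution date and the outcome.
- SAP 8.1 states "Missing data will not be imputed".

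On reporting, SAP 11.7.1.1 puts duration in the AE listing and Sections 11.7.1.1 to 11.7.1.3 name no duration table. SAP 11.7 says that all safety data are both listed and summarised by cohort. SAP Section 8 prescribes mean, SD, median, minimum and maximum for continuous data.

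**The concern.** An event that is unresolved when observation stops has a right-censored duration. The rule turns that lower bound into a figure that looks the same as the duration of an event that ended.

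The study exists because gene-therapy effects may be delayed by months or years. New malignancy, neurologic disorder and autoimmune disorder are among the events collected, and any of these could outlast the follow-up left after onset. The later such an event starts, the smaller its derived duration. A reader comparing durations could take a late, unresolved event for a briefer and milder one than an earlier event that resolved.

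There is a second gap: *date of end of study* is undefined. It could be the subject's own end-of-study or withdrawal assessment (SAP Section 5), or completion of the whole study (Protocol 13.0). Under the second reading, an event in a subject who has already left would accrue days on which nobody observed it. The value would then not even be a valid lower bound.

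**Working it through.** The documents give no sample size, event count or duration figure, so there is nothing to reproduce. The check applies the SAP formula directly.

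**Inputs**

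- Duration = end date − start date + 1 (SAP 10.6).
- End of study at 3 years post-treatment (SAP Section 5): 3 × 365.25 = 1095.75, taken as day 1096.
- Assumption: end of study means the subject's own end-of-study date.

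**1. One never-resolving event, different onset days, followed to day 1096**

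| Onset day | Calculation | Derived duration (days) |
|---|---|---|
| 90 (imported event) | 1096 − 90 + 1 | 1007 |
| 365 (Year 1) | 1096 − 365 + 1 | 732 |
| 395 | 1096 − 395 + 1 | 702 |
| 548 (Year 1.5) | 1096 − 548 + 1 | 549 |
| 730 (Year 2) | 1096 − 730 + 1 | 367 |
| 913 (Year 2.5) | 1096 − 913 + 1 | 184 |
| 1066 | 1096 − 1066 + 1 | 31 |

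The disorder is the same in every row; only the onset day changes. The last row would be listed as shorter than an event that truly resolved after 60 days.

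**2. Withdrawal at Year 2 (day 730)**

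Onset on day 365 gives 730 − 365 + 1 = 366 days. Onset on day 548 gives 730 − 548 + 1 = 183 days. The cut is then the withdrawal date, not Year 3.

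**3. How far the rule matters, by true duration**

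Assumptions not in the documents: onset uniform over Years 1 to 3, no withdrawal, and all events of the same true length.

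| True duration (days) | Mean under SAP rule (days) | Ongoing at end of study |
|---|---|---|
| 30 | 29.4 | 4% |
| 180 | 158 | 25% |
| 365 | 274 | 50% |
| 730 | 365 | 99.9% |
| 1825 | 365 | 100% |

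Short events are barely affected. Events of about 2 and 5 years cannot be told apart, and for both the derived value has a correlation of −1.00 with onset date.

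**4. If duration were summarised**

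Same onset assumption, with exponential true durations; medians in days.

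| True mean | True median | SAP rule | Kaplan-Meier |
|---|---|---|---|
| 30 | 21 | 20 | 21 |
| 180 | 125 | 99 | 125 |
| 365 | 253 | 162 | 252 |
| 730 | 506 | 230 | 507 |
| 1825 | 1265 | 299 | not reached |

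Dropping ongoing events is not a remedy. At a true mean of 730 days, the median of resolved events alone is about 169 days, further from 506 than the 230 days given by the SAP rule.

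**The case against.** The strongest reply is that this is a labelling gap in a descriptive study. Several parts of that reply stand.

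- **Scope.** A reader might infer that the whole duration component measures closeness to Year 3. It does not: events that resolve keep their true duration. The event list also includes exacerbations and unexpected hospitalisations, which may be short. Neither document says how many events will be unresolved.
- **Resolution.** A reader might infer that the rule declares the event resolved. It only sets an end date for one derived variable. The true resolution date and the outcome are collected, and SAP Section 8 provides for listing all eCRF data, so a careful reader could work out that an event is ongoing.
- **Always short.** A reader might infer that delayed events always receive short durations. An unresolved event starting on day 395 gets 702 days; only onset near the cut gives a small value.
- **Contradiction with SAP 8.1.** A specific derivation can take precedence over a general no-imputation statement, and an end that has not yet happened is arguably not missing data. The two sit awkwardly together, but this is not a clear contradiction.
- **Overwritten dates.** Protocol 6.9 also lets follow-up stop at stability, and no provision says that dates after end of study reach the locked database. That a known later date would be replaced is possible, not established.
- **Output.** The only output named for duration is a listing.

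The last point limits the harm without removing it. The listing is where this endpoint component will be read, and the SAP specifies no marker beside the number. The general wording of SAP 11.7, with the descriptive statistics in Section 8, leaves a summary of duration open.

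**Conclusion.** The point holds for events ongoing at end of study and for no others. For these, SAP 10.6 reports a right-censored value of a primary-endpoint component as if it were complete. In the worked example the same never-resolving event is given anything from 31 to 1007 days according to its onset day.

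Those figures assume that end of study is the subject's own date, at day 1096. The overall effect on the report cannot be sized, because the documents give no event counts; the averages and medians above illustrate assumed onset and duration patterns. No hypothesis test is affected. It is still worth correcting before database lock, because the rule gives a misleading value by design and the correction costs almost nothing.

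**What to change.** Replace the sentence on ongoing events in SAP 10.6 with:

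> For AEs ongoing at the subject's last contact, the end date is left blank and duration is shown as ≥ (date of last contact − AE Start date + 1) days, ongoing. If follow-up under Protocol 4.3 or 6.9 gives a later resolution date before database lock, that date is used. Any summary of duration treats ongoing AEs as right-censored (e.g. Kaplan-Meier) and states the number ongoing; they are neither counted as resolved nor excluded.

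Anchoring the rule to last contact also removes the ambiguity about the end-of-study date. One added sentence should say how the rule stands in relation to SAP 8.1.

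The cost is SAP wording and a flag in the AE dataset and listing; no new data are needed. The downside is that some AEs will carry a lower bound instead of a single duration. With few events or many still ongoing, a Kaplan-Meier median may not be reached, and the listing with its flag would then carry the information.

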11.1 Subject Disposition

Number of subjects in enrolled, screen failures and in FAS population, number and percentage for subjects who completed the study, study duration (years)^[10.5], number of subjects who discontinued the study early along with their reasons will be summarized by cohort. Reason for discontinuation will be displayed in the descending order of "Total" column.

Reason for not completing the study includes:

- A medical decision is made to resume or initiate
- Lost to Follow up
- Withdrawal of consent by Subject
- Adverse event
- Major Protocol deviation prior to treatment

Confidential

Created using Template: [REDACTED]

Page 10 of 16

- Physician Decision
- Study Terminated by Sponsor
- Other

Percentages will be based on FAS population.

Number of subjects who did not meet the IE criteria will be summarized separately. Percentages will be based on enrolled population.

Subject disposition information, status of inclusion exclusion criteria will be listed by subject.

11.2 Visit Attendance

Number and percentage of subjects who attended each visit (Screening, Year 1, Year 2, and Year 3 (EOS)) will be summarized by cohort. Percentages will be based on FAS Population.

11.3 Protocol Deviations

Significant protocol deviations:

Number and percentage of subjects with any significant protocol deviation along with their categories will be summarized by cohort.

Percentages will be based on FAS population.

All protocol deviations reported will be listed by dose cohort and subjects. All the significant protocol deviations will be listed separately along with their impact on the analysis and corresponding mitigation action items.

11.4 Subject Demographics

Subject demographics will be summarized by cohort. Categorical and continuous variables will be provided in the same table. The following variables will be presented: age (years), sex, ethnicity and race.

Percentages are based on FAS population.

Subject demographics will be listed by subject.

11.5 Concomitant Medications

Number and percentage of subjects who have taken any medication and number of medications will be summarized by cohort. Number of patients who have taken any medication will be classified by Therapeutic Main group (ATC Level 2) and Chemical Substance group (ATC Level 5). The therapeutic main group and chemical substance group will be displayed in the descending order of frequency in “Total”. Medications will be coded using the World Health Organization’s Drug-Dictionary (WHODrug Dictionary) version B2 Enhanced VSEP 2017 or higher.

Percentages will be based on FAS population.

All medications will be listed by subject and therapeutic subgroup.

11.6 Extent of Exposure

IMP administration data will be listed by subject for FAS population. Subjects will be grouped by cohort.

11.7 Safety Analyses

The long-term safety of ADVM-043 is to be assessed by determining the type, frequency and percentages, severity, duration, and relationship to ADVM-043 of adverse events (AEs) of interest and serious adverse events (SAEs) related to ADVM-043. All safety data will be listed and summarized by cohort using the FAS population.

Only AEs of interest will be summarized.

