11.7.1.3 Summary of Adverse Events by Severity

Number and percentage of subjects in each system organ class, preferred term, and intensity (Grade 1-5) will be summarized by severity for adverse events of interest and cohort. System organ class and preferred term will be displayed by descending order of frequency in “Total”.

12 Changes to Planned Analyses

No changes from the analysis defined in protocol.

13 Index of Tables, Listings and Graphs

Refer [REDACTED] for the list of Tables, Listings and Graphs.

14 References

Provide list of references used to create this document.

- ICH. ICH Harmonized Tripartite Guideline: Statistical Principles for Clinical Trials E9. 1998.
- ASA. Ethical Guidelines for Statistical Practice. Prepared by the Committee on Professional Ethics. 1999.
- ICH. ICH Harmonized Tripartite Guideline: Structure and Content of Clinical Study Reports E3. 1995.

15 Appendices

Not Applicable

16 Change Log

Version	Authored by	Change Date	Change Details	Reviewed by	Review Date
1.0	[REDACTED]	[REDACTED]	First Draft	[REDACTED]	[REDACTED]

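### SAP 10.6 and 11.7 limit reporting to AEs of interest, which leaves out the second class of the primary endpoint: related SAEs outside that list

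*SAP*

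**What the plan says.** SAP 7.1 and Protocol 2.2.1 define one primary endpoint with five attributes (type, frequency, severity, duration, relationship) for two classes of event: "adverse events (AEs) of interest and serious adverse events (SAEs) related to ADVM-043".

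The SAP then narrows this twice:

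- SAP 10.6: "Only AEs of interest will be collected and reported in the current study".
- SAP 11.7: "Only AEs of interest will be summarized". The sentence just before it says the opposite: "All safety data will be listed and summarized by cohort using the FAS population".

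Two severity instructions carry the same limit. The worst-grade rule in SAP 10.6 reads "Subjects with the same AE of interest and different severities will be flagged for the most intense severity", and the Grade 1-5 table in SAP 11.7.1.3 "will be summarized by severity for adverse events of interest and cohort".

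Elsewhere related SAEs are in scope. Protocol 6.3 and 6.8 require them to be collected and recorded, and the SAP 5 schedule records them at every assessment. Row 5 of the overall table in SAP 11.7.1.1 counts them, and SAP 11.7.1.2 orders a SOC/PT table of related serious AEs without the of-interest limit.

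**The concern.** The analyst has two incompatible instructions on whether a related SAE outside the AE-of-interest list enters the summaries, and the SAP does not say which prevails. Read literally, the 11.7 sentence removes part of the primary endpoint from every table. That would also be an undeclared departure: Protocol 8.0 asks for descriptive analyses of all data, and SAP 12 declares no change from the protocol.

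Even on the favourable reading, severity is an attribute of both classes but the visible text tabulates the grade distribution for only one. Long-term safety is the study's only objective. Whether a related SAE is counted should not depend on which sentence a programmer follows.

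**Working it through.** No formula in the plan applies. The check sets the texts side by side and counts which planned summaries a related SAE reaches when it falls outside all four categories.

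**Source of the mismatch.** Protocol 6.2 has a sentence limiting AE collection to AEs of interest. Protocol 6.3 follows with a parallel sentence admitting SAEs that are related. Together they cover both endpoint classes. SAP 10.6 carries over the first and has no counterpart to the second.

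**Which events are exposed.** The event must meet all three conditions:

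- It is serious under Protocol 6.3.
- It is rated related. For events in this study SAP 10.6 says "AE: includes Definitely and Likely Related Adverse Events".
- It is outside new malignancy, neurologic disorder, rheumatologic or other autoimmune disorder, and unexpected hospitalization.

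The fourth category absorbs much of the hospitalization criterion. What remains is chiefly a related death, life-threatening event, disability or congenital anomaly with no unexpected hospitalization and outside the other three categories.

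**Overall table (SAP 11.7.1.1), six rows.**

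| Row | Table instructions followed | 11.7 sentence literal |
|---|---|---|
| 1. AEs of interest | no | no |
| 2. Related AEs | yes | no |
| 3. Grade 3 or higher | if Grade 3 or higher | no |
| 4. Serious AEs | yes | no |
| 5. Related serious AEs | yes | no |
| 6. Fatal AEs | if fatal | no |

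Rows reached under the table instructions:

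- Grade 1 or 2: 3 of 6 (rows 2, 4, 5).
- Grade 3 or 4, not fatal: 3 + 1 = 4 of 6.
- Fatal: 3 + 1 + 1 = 5 of 6.

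Under the literal reading: 0 of 6.

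**SOC/PT summaries.** SAP 11.7.1.2 gives four: AEs of interest, related AEs of interest, serious AEs of interest, and related serious AEs. SAP 11.7.1.3 gives one more, by grade. Total 4 + 1 = 5. The event reaches 1 of 5 (related serious AEs) under the table instructions and 0 of 5 under the literal reading.

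**Grade distribution.** SAP 11.7.1.3 covers AEs of interest only and has no repeat clause like the one in 11.7.1.2. For these events 0 of 5 grades are tabulated on either reading. Row 3 of 11.7.1.1 does not fill the gap. It is a single threshold, and it pools AEs of interest of any causality with related SAEs.

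**What survives in any case.** SAP 8 lists all eCRF data and SAP 11.7.1.1 lists all AEs, so each event and its grade would still appear in listings.

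**The case against.** The strongest reply is that the SAP largely resolves the conflict itself. The first sentence of 11.7 names both classes, and 11.7.1.1 and 11.7.1.2 then order related-SAE outputs explicitly. Getting to zero rows means ignoring two specified outputs. This makes the literal reading the less likely one, but it does not remove the contradiction or say which text governs.

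Second, the severity gap is small under the protocol's own definitions. Protocol 6.4 puts indicated hospitalization and disabling events at Grade 3, life-threatening consequences at Grade 4 and death at Grade 5. A related SAE should therefore nearly always be Grade 3 or higher, the Grade 1 or 2 case is largely hypothetical, and row 5 is close to a Grade 3-or-higher count. This stands as a limit on size: what is mainly lost is the Grade 3 versus Grade 4 split by SOC and PT. It does not supply the severity distribution that the endpoint names.

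Third, SAP 13 refers to a redacted document "for the list of Tables, Listings and Graphs", so a separate severity table for related SAEs cannot be excluded. That stands. The omission is established only for the visible text; the wording conflict does not depend on the redaction.

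Fourth, in a small descriptive study a listing may be enough for a handful of events, and the worst-grade flag matters only when a subject has the same event at more than one grade. Both points are fair and lower the stakes. The SAP nevertheless chose to tabulate severity for one endpoint class and gives no reason for treating the other differently.

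**Conclusion.** The concern holds. As written, SAP 10.6 and 11.7 exclude a class of event that the primary endpoint includes and that the SAP's own tables count. A related SAE outside the list reaches 3, 4 or 5 of the 6 overall rows and 1 of 5 SOC/PT summaries if the table instructions govern, and none if the 11.7 sentence governs. It is absent from the visible Grade 1-5 table either way.

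These counts measure coverage in the text, not an effect on a result. No event rate or sample size is given, so the number of subjects affected cannot be stated; it is likely to be small. Confidence is high for the wording conflict. For the missing severity table, the conclusion is confined to the unredacted text. The correction should be made before database lock.

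**What to change.** 1. In SAP 10.6 and 11.7, extend each restriction so that it names both endpoint classes, as SAP 7.1 does: "adverse events (AEs) of interest and serious adverse events (SAEs) related to ADVM-043".
2. Extend the worst-severity flag in SAP 10.6 to related SAEs.
3. Extend the Grade 1-5 table in SAP 11.7.1.3 to related SAEs, in the same table or a parallel one. If the redacted index already contains such a table, refer to it in 11.7.1.3.

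A sensible companion edit is to extend the SAP 10.6 sentence on importing continuing events from the previous study, which also names only AEs of interest, to related SAEs.

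The cost is two SAP sentences, one flag definition and one extended or parallel table. No protocol change or new data collection is needed, because Protocol 6.6 already collects seriousness, severity and relationship.
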